I will maintain adequate source documents and record all observations, treatments and procedures pertinent to trial subjects in their medical records. I will accurately complete and submit the electronic case report forms supplied by the Sponsor in a timely manner. I will ensure that my facilities and records will be available for inspection by representatives of FUJIFILM Pharmaceuticals U.S.A., Inc. (FPHU), Westat, the IRB or local regulatory authorities. I will ensure that I and my staff are available to meet with representatives of FPHU and Westat during regularly scheduled monitoring visits.

I will notify the Medical Monitor within 24 hours of any serious adverse events. Following this notification, a written report describing the serious adverse event will be provided to FPHU/Westat as soon as possible, but no later than 5 days following the initial notification.

Principal Investigator's Signature

Date

Principal Investigator's Name (Print)

SYNOPSIS

Sponsor: FUJIFILM Pharmaceuticals U.S.A., Inc.	Protocol Number: FF1050101US101
Name of Study Drugs (reagents): FF-10501-01	Protocol Title: A Phase 1/2a Dose-escalation Study of FF-10501-01 for the Treatment of Advanced Hematologic Malignancies
Name of Active Ingredient: 4-carbamoylimidazolium-5-olate	Phase of Development: Phase 1/2a
Primary Objective:	

 • To determine the safety and tolerability in subjects who receive FF-10501-01 for the treatment of advanced hematologic malignancies 	
Secondary Objectives:	

 • To determine the overall response rates • To evaluate the proportion of subjects who achieve hematologic improvement in peripheral blood or bone marrow blast count • To evaluate progression-free survival (PFS) • To evaluate overall survival (OS) • To evaluate the pharmacokinetics of FF-10501 and M1 • To evaluate xanthosine monophosphate (XMP) as a pharmacodynamic marker 	
Methodology:	

This is a Phase 1/2a, dose-escalation study of FF-10501-01 for the treatment of advanced hematologic malignancies.
 
A total of up to N= 68 subjects will be enrolled in the study. Subjects with acute myelogenous leukemia (AML) (Phase 1 only), myelodysplastic syndrome (MDS), and chronic myelomonocytic leukemia (CMML) will be included.
 
Major selection criteria are: age \geq 18 years, confirmed MDS/CMML or AML (Phase 1 only for AML) with documented disease progression following previous therapy, or subjects with AML \geq 60 years of age who are not candidates for other therapies (Phase 1 only). Subjects must be \geq 3 weeks beyond chemotherapy, radiotherapy, major surgery, or other experimental treatments, and recovered from all acute toxicities (\leq Grade 1), have adequate renal and hepatic function, and no known history of significant cardiac disease.
	

Phase 1:
 
14-day Schedule: Following Screening, a total of 6 cohorts of 3 subjects each received oral doses of 50, 100, 200, 300, 400 or 500 mg/m² BID per day (100, 200, 400, 600, 800 or 1000 mg/m²/day) for 14 days, followed by 14 days off, repeated every 28 days (= 1 cycle). Three events of drug-related atrial fibrillation (Grade 2) were reported in 2 subjects at a dose of 500 mg/m² BID (Cohort 6). Study drug was suspended in both subjects and all events resolved with oral metoprolol treatment. These events were medically important events and thus met the definition of dose-limiting toxicity (DLT). No further enrollment was made at this dose level. The maximally tolerated dose (MTD) was declared at 1 dose level below the dose eliciting DLT, 400 mg/m² BID, and this
	

Sponsor: FUJIFILM Pharmaceuticals U.S.A., Inc.	Protocol Number: FF1050101US101
--	---

Methodology continued:

cohort was expanded to 6 subjects. No DLTs have been observed in N=7 total subjects treated at 400 mg/m² BID x 14 days.

21-day Schedule: At the MTD of 400 mg/m² BID, Cohort 7 was added to extend the BID dosing schedule to 21 days followed by 7 days off, repeated every 28 days (=1 cycle) (Amendment 3).

28-day Schedule: At the MTD of 400 mg/m² BID, Cohort 8 was added to extend the BID dosing schedule to 28 days continuous dosing each 28 days (=1 cycle) (Amendment 4).

DLT is defined as Grade 4 hematologic toxicity lasting 7 days or more; Grade 3 nonhematologic toxicity of any duration not amenable to supportive care; failure of platelets, absolute neutrophil count (ANC), or hemoglobin (Hb) to recover to Grade 1 within 12 weeks despite use of platelet and red blood cell (RBC) transfusions and/or growth factors; febrile neutropenia (defined as ANC<1000/mm³ with a single temperature of > 38.3°C or sustained temperature of ≥ 38°C for over one hour); Grade 3 thrombocytopenia associated with bleeding; or other important medical event.

For all subject cohorts, if 1 of 3 subjects per cohort experiences DLT, the cohort will be expanded to 6. If 2 of 6 subjects per cohort experience DLT, all further dose escalation will stop. If 0 of 3 or ≤ 1 of 6 subjects per cohort experience DLT by Day 28 following dosing of FF-10501-01, dose escalation will proceed to the next cohort. At the MTD of 400 mg/m² BID, the longest schedule of administration below the schedule of administration eliciting DLT will be declared the recommended Phase 2 dose (RP2D) and schedule. A total of 6 subjects will be treated at the RP2D and schedule. No intra-subject dose escalation will be allowed from previous dose levels/schedules of administration until at least one subject has completed Cycle 1 at the longer schedule of administration (e.g., 21 or 28 days) with no Grade 2 or greater toxicities observed. Additionally, patients currently on study will have the option to extend their current dosing schedule to 21 days, followed by 7 days off, repeated every 28 days (=1 cycle), or 28 days of continuous dosing, whichever is chosen as the best schedule, if seen in the patient's best interest by the principal investigator. Dose level adjustments for DLT will be made. Subjects who experience DLT at the first dose level, 50 mg/m² BID, will not be dose-reduced. Up to 48 subjects are planned for Phase 1.

Phase 2a: Once 6 subjects are treated at the RP2D and schedule in Phase 1, 1 additional cohort will enroll 20 subjects with MDS/CMML who have relapsed from, or are refractory to, prior hypomethylating agent (HMA) therapy. Subjects enrolled in Phase 1 at the RP2D and schedule and who meet the Phase 2a selection criteria will count towards the Phase 2a accrual. Dose level adjustments for adverse events will be made.

During the study, a Safety Review Committee, consisting of the actively recruiting investigators, the Medical Monitor, and FPHU, will review data from each cohort on an ongoing basis.

Sponsor: FUJIFILM Pharmaceuticals U.S.A., Inc.	Protocol Number: FF1050101US101
Methodology continued:	

Subjects on the 21-day schedule will receive FF-10501-01 on a BID schedule. For all subjects on the 21-day dosing schedules, blood samples for pharmacokinetic assessment of FF-10501 and M1 in plasma will be collected on Cycle 1 Day 1 pre-dose (any time), between 0.5-1 hr post-dose, and between 2-4 hr post-dose, and Day 15 pre-dose (within 15 minutes prior to dosing), between 0.5-1 hr post-dose, and between 2-4 hr post-dose.
 
Blood concentration of xanthosine monophosphate (XMP) will be assessed as a pharmacodynamic endpoint.
 
For subjects on the 21-day dosing schedules, blood samples for XMP assessment will be collected on Cycle 1 Day 1 pre-dose (any time), between 0.5-1 hr post-dose, and between 2-4 hr post-dose, and Day 15 pre-dose (within 15 minutes prior to dosing), between 0.5-1 hr post-dose, and between 2-4 hr post-dose.
 
Disease assessments, including analysis of blood and bone marrow aspirates, will be performed at the end of Cycle 1 and Cycle 3 and every 2 cycles thereafter. Disease assessments may be performed at other time points at the discretion of the investigator.
 
Subjects who demonstrate objective response (OR) or stable disease (SD) will be allowed to continue therapy with FF-10501-01 until progression of disease, observation of unacceptable adverse events, intercurrent illness or changes in the subject's condition that prevents further study participation.
 
Blood for hematology, platelet and serum chemistry determinations will be collected within 28 days of Cycle 1 Day 1, on Days 1, 8, 15 and 22 of Cycle 1, on Day 1 of each subsequent cycle and at the End of Study Visit. Urine will be collected for urinalysis within 28 days of Cycle 1 Day 1, on Day 1 of each subsequent cycle and at the End of Study Visit.
	

Number of Subjects and Centers: Phase 1: Up to 48 subjects are planned for the dose-escalation phase. Phase 2a: A total of 20 subjects with MDS/CMML treated at the RP2D are planned, including MDS/CMML subjects treated at the RP2D in Phase 1. Therefore, up to 68 total subjects are planned.
 
The study will be conducted at up to seven sites.
	

Duration of Study: The accrual phase for the Phase 1 dose escalation phase is expected to be 12 – 18 months. The expected accrual for the Phase 2a expansion phase is expected to be 6 – 12 months, with the last subject followed up to 6 months, for a total study duration of 30 – 36 months. The anticipated accrual rate for the Phase 2a portion is 4 – 5 subjects per month.
	

Sponsor: FUJIFILM Pharmaceuticals U.S.A., Inc.	Protocol Number: FF1050101US101
Inclusion Criteria:	

 • Males and females \geq 18 years of age • Subjects with confirmed advanced hematologic malignancies: 
 • Phase 1: 
 • High-risk MDS/CMM (defined as \geq 10% peripheral blood or marrow blasts and/or International Prognostic Scoring System [IPSS] score \geq 1.5) and relapsed or refractory to prior therapy • AML relapsed or refractory to prior therapy, or \geq 60 years of age and not a candidate for other therapies • Phase 2a: 
 • MDS/CMM, relapsed from, or refractory to, prior HMA therapy; the latter defined as failure to achieve clinical remission (CR), partial remission (PR) or hematologic improvement (HI) after previous HMA therapy (\geq 4 cycles of azacitidine or decitabine), or progression during, or toxicity to, previous HMA therapy precluding further HMA treatment, and 
 • Bone marrow blast count \geq 10% or peripheral blast count \geq 5%, or IPSS-R score \geq 3.5 • At least 3 weeks beyond the last chemotherapy, targeted anticancer agent, major surgery or experimental treatment and recovered from all acute toxicities (\leq Grade 1). Hydroxyurea used to control peripheral blast counts is permitted up to Day 7 of treatment on study. • Adequate performance status: Eastern Cooperative Oncology Group (ECOG) \leq 2 • Adequate renal and hepatic function: 
 • Creatinine \leq 2.0 mg/dL, or calculated creatinine clearance \geq 45 mL/minute per the Cockcroft-Gault formula • Total bilirubin \leq 2 times the upper limit of normal (ULN) • ALT and AST \leq 2 times ULN • Negative serum pregnancy test within 14 days prior to the first dose of study therapy for women of child-bearing potential (WCBP), defined as a sexually mature woman who has not undergone a hysterectomy or who has not been naturally post-menopausal for at least 24 consecutive months (i.e., who has had menses any time in the preceding 24 consecutive months). Sexually active WCBP and male subjects must agree to use adequate methods to avoid pregnancy (oral, injectable, or implantable hormonal contraceptive; tubal ligation; intra-uterine device; barrier contraceptive with spermicide; or vasectomized partner) throughout the study and for 28 days after the completion of study treatment. • Ability to provide written informed consent 	

Sponsor: FUJIFILM Pharmaceuticals U.S.A., Inc.	Protocol Number: FF1050101US101
Exclusion Criteria:	

 Known history of active coronary artery disease, angina, myocardial infarction, congestive heart failure, cardiac arrhythmia or any other type of heart disease present within the last 6 months Known family history of hereditary heart disease QT interval corrected for rate (QTc) > 450 msec on the electrocardiogram (ECG) obtained at Screening Concomitant medication(s) that may cause QTc prolongation or induce Torsades de Pointes, with the exception of anti-microbials that are used as standard of care to prevent or treat infections and other such drugs that are considered by the Investigator to be essential for the care of the patient Presence of active central nervous system (CNS) leukemia. Subjects adequately treated for CNS leukemia documented by 2 consecutive cerebrospinal fluid samples negative for leukemia cells are eligible. Subjects with no history of CNS leukemia will not be required to undergo cerebrospinal fluid sampling for eligibility. Known positive for human immunodeficiency virus (HIV), hepatitis B virus surface antigen (HBsAg), or hepatitis C virus (HCV) Active infection requiring intravenous (IV) anti-infective usage within the last 7 days prior to study treatment Any other medical intervention or other condition which, in the opinion of the Principal Investigator, could compromise adherence to study requirements or confound the interpretation of study results Pregnant or breast-feeding Treatment with any investigational product within 28 days prior to Screening 	
Criteria for Evaluation:	

Safety: Safety will be assessed through the monitoring of adverse events (AEs), clinical laboratory parameters (hematology, serum chemistry, urinalysis), vital sign measurements, ECGs and physical examinations. Adverse events will be classified according to the Medical Dictionary for Regulatory Affairs (MedDRA) and graded according to the National Cancer Institute Common Terminology Criteria for Adverse Events (NCI CTCAE) version 4.03.
 
Efficacy: Efficacy assessment for AML will be performed using a modification of the recommendations of the International Working Group for Diagnosis, Standardization of Response Criteria, Treatment Outcomes, and Reporting Standards for Therapeutic Trials in Acute Myeloid Leukemia. Efficacy assessments for subjects with MDS or CMML will be performed using a modification of the International Working Group Response Criteria in Myelodysplasia. Efficacy assessments for any subject may be performed at other time points at the discretion of the investigator.
 
Pharmacokinetics: Pharmacokinetic determinations will be performed.
 
Pharmacodynamics: XMP will be determined in peripheral blood.
	

Sponsor: FUJIFILM Pharmaceuticals U.S.A., Inc.	Protocol Number: FF1050101US101
Investigational Product:	
FF-10501-01 is an oral antimetabolite anticancer drug. It is a competitive inhibitor of inosine 5'-monophosphate dehydrogenase (IMPDH). FF-10501-01 is supplied in 50 and 200 mg tablets for oral administration. FF-10501-01 should be stored at room temperature (20 – 25 °C).	
FF-10501-01 is manufactured for FPHU by Patheon (Missisauga, Ontario, Canada) and will be provided by the sponsor (FPHU).	
Reference Therapy: None	
Statistical Methods:	
Safety Endpoint Analyses:	
Safety endpoints for AEs include the following: incidences of all treatment-emergent adverse events (TEAEs) and all serious adverse events (SAEs); incidences of TEAEs and SAEs by severity; incidences of TEAEs and SAEs by relationship to study medications; incidences of all Grade 3 and 4 TEAEs and by severity and relationship to study medications; and discontinuation of subjects from the study due to AEs or death. Safety endpoints for AEs, clinical laboratory tests, vital signs, ECGs and physical examinations will be specified in the statistical analysis plan. All safety endpoints will be summarized using descriptive statistics.	
Efficacy Endpoint Analyses:	
The primary endpoint will be the proportion of subjects who achieve an objective response (OR) as best response (CR, CRi or PR). Each dose cohort will be analyzed independently. For the primary efficacy endpoint, OR by disease type (AML, MDS, CMML) will be summarized using the number and percentage of subjects with an OR. The proportion of subjects with hematologic improvement in peripheral blood or bone marrow blast count and 90% confidence intervals will be estimated. For secondary endpoints, PFS and OS, curves will be estimated for each dose cohort and disease type using Kaplan-Meier product-limit estimates.	
Pharmacokinetic and Pharmacodynamic Endpoint Analyses: Analysis plans will be described in the written plans provided by the laboratories performing the analyses.	

TABLE OF CONTENTS

INVESTIGATOR SIGNATURE PAGE	2
SYNOPSIS	3
LIST OF FIGURES	12
LIST OF APPENDICES	12
LIST OF ABBREVIATIONS	13
1. INTRODUCTION	15
1.1. FF-10501-01 Background.....	15
1.2. SM-108 Preclinical Summary.....	15
1.3. SM-108 Previous Human Experience.....	16
1.3.1. Phase 1 Study in Advanced Solid Tumors or Hematologic Malignancies	16
1.3.2. Phase 2 Study in Advanced Lung Cancer.....	16
1.3.3. Phase 2 Study in Advanced Hematologic Malignancies	17
1.4. FF-10501-01 Preclinical Pharmacology	18
1.4.1. Induction of differentiation in myeloid leukemia cell lines.....	18
1.4.2. In Vitro Growth Inhibition in Myeloid Leukemia Cell Lines.....	19
1.4.3. Inhibition of Growth in an Azacitidine-resistant Cell Line	20
1.4.4. FF10501-01 Mechanism of Action.....	20
1.4.5. Anti-tumor Activity in a Human Myeloid Leukemia SKM-1 Xenograft Model in Mice	21
1.5. FF-10501-01 Preclinical Pharmacokinetic, Metabolism, Excretion.....	22
1.5.1. Single Oral Dose Pharmacokinetics.....	22
1.5.2. Multiple Dose Oral Pharmacokinetics	22
1.5.3. Distribution	23
1.5.4. Metabolism	23
1.5.5. Excretion	23
1.6. Toxicology	24
1.6.1. Repeat-dose Toxicity Studies in Rats	24
1.6.2. Repeat-dose Toxicity Studies in Dogs.....	24
1.6.3. Genotoxicity.....	25
1.6.4. Phototoxicity	25
1.7. FF-10501-01 Experience in Humans	25
1.7.1. Japan Phase 1 Study.....	25
1.7.2. U.S. Phase 1/2a Study	26
1.8. Dose Rationale.....	27
2. STUDY OBJECTIVES	27
2.1. Primary Objective:	27
2.2. Secondary Objective:	27
3. INVESTIGATIONAL PLAN	28
3.1. Overall Study Design.....	28
3.2. Number of Subjects and Centers.....	30
3.3. Duration of Study.....	30
3.4. Criteria for Termination of the Study	30
4. STUDY POPULATION	31
4.1. Inclusion Criteria	31

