7.2.3. Efficacy Endpoints

7.2.3.1. Primary Efficacy Endpoint

To evaluate the proportion of subjects with objective response achieved within 3 cycles of treatment with FF-10501-01 (i.e., within 3 months) in subjects with relapsed/refractory AML or relapsed/refractory high-risk MDS or CMML.

- **Subjects with AML**

Objective responses for subjects with AML include complete remission (CR), complete remission with incomplete blood count recovery (CRi) and partial remission (PR) as defined above.

- **Subjects with MDS**

Objective responses for subjects with high-risk MDS include complete remission (CR), partial remission (PR), and marrow CR as defined above.

- **Subjects with CMML**

Objective responses for subjects with CMML include complete remission (CR), partial remission (PR) and marrow CR as defined above.

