8.3.2.1. Primary Efficacy Endpoint

The primary efficacy endpoint is the proportion of subjects treated at the MTD in each disease cohort (AML, MDS or CMML) with objective response (OR) within 3 cycles of study drug (i.e., within 3 months). For subjects with AML, OR is CR, CRi, or PR, as defined above. For subjects with MDS or CMML, OR is CR, PR or marrow CR, as defined above. The proportion of subjects in each disease cohort treated at the MTD will be summarized, and 90% confidence intervals will be estimated.

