3.3. Analysis of Efficacy

All efficacy analyses will be conducted for Phase 1 subjects by dose cohort, if applicable, and for Phase 2a subjects by MDS/CMMML disease cohort at the RP2D and schedule (400 mg/m² BID x 21 days, repeated every 28 days) using the Per Protocol Population (PPS dataset).

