3.3.1. Primary Endpoints

The primary efficacy endpoint is the proportion of subjects with objective response achieved within 3 cycles of treatment with FF-10501-01 (i.e., within 3 months) in subjects with relapsed/refractory AML or relapsed/refractory high-risk MDS or CMMML.

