4.1.4. Primary Efficacy Summaries

- Summary of Subject's Disease Response and 90% Confidence Intervals - AML
- Summary of Subject's Disease Response and 90% Confidence Intervals - MDS/CMM

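### The synopsis defines the primary efficacy endpoint differently from Protocol 7.2.3.1 and 8.3.2.1, and the synopsis, protocol body and SAP report it in different groups

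*Protocol*

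**What the plan says.** **Definition.** The synopsis (Efficacy Endpoint Analyses) reads: "The primary endpoint will be the proportion of subjects who achieve an objective response (OR) as best response (CR, CRi or PR". That is one list for all three diseases. Protocol 7.2.3.1 sets a limit of 3 cycles, glossed as 3 months, and lists components by disease. For CMML: "Objective responses for subjects with CMML include complete remission (CR), partial remission (PR) and marrow CR as defined above"; MDS has the same three. Protocol 8.3.2.1 agrees: "For subjects with MDS or CMML, OR is CR, PR or marrow CR, as defined above". For AML both sections count CR, CRi or PR. SAP 3.3.1 has "objective response achieved within 3 cycles of treatment with FF-10501-01 (i.e., within 3 months" and lists no components.

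**Group.** The synopsis analyses each dose cohort independently and says "OR by disease type (AML, MDS, CMML) will be summarized using the number and percentage of subjects with an OR". Protocol 8.3.2.1 takes the "proportion of subjects treated at the MTD in each disease cohort (AML, MDS or CMML" and names no analysis set. SAP 3.3 reports Phase 1 by dose cohort and Phase 2a at the recommended dose and schedule (RP2D), "using the Per Protocol Population (PPS dataset". Its planned table is headed "Disease Response and 90% Confidence Intervals - MDS/CMM", which does not say whether the two diseases are pooled.

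**Size.** Protocol 8.1 allows up to 36 Phase 1 subjects in 6 cohorts. Protocol 3.1 and 3.2 and SAP 2.1 allow 48, in up to 8 cohorts per SAP 2.1. Protocol 8.1 and SAP 2.1 call the 20 Phase 2a subjects additional. Protocol 3.1 and 3.2 and SAP 1.3.1 count Phase 1 RP2D subjects towards the 20. Protocol 3.1 and SAP 1.3.1 require those subjects to meet the Phase 2a criteria; Protocol 3.2 does not say so.

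**The concern.** Phase 2a enrols only MDS and CMML. The synopsis list omits marrow CR, which Protocol 7.2.2.2 defines for those diseases, and includes CRi, which is defined only for AML (7.2.2.1). It also has no time limit, while disease assessment continues every two cycles after Cycle 3.

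The study is unblinded. If the texts are not reconciled, the component list, window and denominator could be settled after the responses are known. In a pooled set of 20, each subject whose only response is marrow CR moves the rate by 1/20 = 5 percentage points.

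**Working it through.** The plan derives no sample size, power or error rate from this endpoint, so there is no figure of its own to reproduce.

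**1. Texts side by side**

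| Source | Time limit | MDS/CMML components | Reporting group | Analysis set |
|---|---|---|---|---|
| Synopsis | none | CR, CRi, PR | each dose cohort; by disease type | not named |
| Protocol 8.3.2.1 | 3 cycles (3 months) | CR, PR, marrow CR | MTD, by AML, MDS, CMML | not named |
| SAP 3.3, 3.3.1 | 3 cycles (3 months) | not listed | Phase 1 by dose cohort; Phase 2a at RP2D and schedule | PPS |

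The MTD, 400 mg/m² BID, was given on 14-, 21- and 28-day schedules (Protocol 3.1). The RP2D is that dose on the 21-day schedule only (SAP 1.3.1). The second and third rows are therefore different groups.

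**2. Effect on reported responses.** Inputs from Protocol 1.7.2: 33 treated (25 AML, 8 MDS); one marrow CR in an MDS subject at 400 mg/m² BID × 14 days after 1 cycle; three AML partial remissions after 1–3 cycles. No MDS CR or PR is reported, and I take the count as zero.

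Let k be the number of MDS subjects at 400 mg/m² BID, which is not given. Protocol 1.7.2 also reports a platelet response in a subject on the 21-day schedule at that dose. Hematologic improvement is defined for MDS only (7.2.2.2), so k is probably at least 2. Range: 2 to 8.

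Intervals are exact (Clopper-Pearson) 90%; the supplied text names no method. The lower limit for 1/k is 1 − 0.95^(1/k), and the upper limit for 0/k is 1 − 0.05^(1/k).

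| k | 8.3.2.1 components | Synopsis components |
|---|---|---|
| 2 | 1/2 = 50% (2.5–97.5) | 0/2 = 0% (0–77.6) |
| 4 | 1/4 = 25.0% (1.3–75.1) | 0/4 = 0% (0–52.7) |
| 8 | 1/8 = 12.5% (0.6–47.1) | 0/8 = 0% (0–31.2) |

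For AML at all dose levels, 3/25 = 12.0% (3.4–28.2) under either definition. The marrow CR also came after 1 cycle, so the 3-cycle limit changes no response reported so far.

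The group matters for the same subject, who is inside the MTD group of 8.3.2.1. Under SAP 3.3 the subject falls in a Phase 1 cohort on the 14-day schedule, outside Phase 2a.

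**3. Cycles against months.** Three cycles are 3 × 28 = 84 days. Protocol 5.4.2 allows a delay of up to 14 days, and longer in some cases after two cycles. One 14-day delay gives 84 + 14 = 98 days, more than three months of at most 31 days (3 × 31 = 93). The two limits can then disagree.

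**4. Analysis set.** The PPS needs a valid baseline and at least one post-treatment assessment (Protocol 8.2, SAP 2.2.3). Illustration, assuming 4 responders among 20 treated:
- Dropping 0, 2 or 4 unassessed subjects gives 4/20 = 20%, 4/18 = 22.2% or 4/16 = 25%. This exclusion cannot lower the rate.
- Dropping one subject for lack of a valid baseline gives 4/19 = 21.1% if a non-responder, or 3/19 = 15.8% if a responder. The second is possible because CR rests on absolute thresholds.

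**5. Size.** 6 × 6 = 36 (Protocol 8.1); 8 × 6 = 48 (SAP 2.1); 48 + 20 = 68, a ceiling on either reading of the 20.

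**The case against.** The best defence is that the synopsis is only a summary. Two protocol sections and the SAP agree on the window. SAP 3.3.1 follows the 7.2.3.1 sentence closely, so a reader would naturally take the components from there. Safety is the primary objective, response is secondary (Protocol 2.2), and SAP 2.4.2 plans no test. Using the PPS fills a gap in 8.3.2.1 and contradicts nothing. SAP 2.1 already has 48 subjects in 8 cohorts.

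Much of this stands. The SAP is incomplete on components but does not contradict the protocol body. Reporting on all treated subjects is an improvement, not the correction of an error. The defence does not remove a synopsis list that does not fit the Phase 2a population, three different reporting groups, or a Phase 1 size in Protocol 8.1 that disagrees with Protocol 3.1 and 3.2.

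A reader might also infer that the PPS can only keep or raise the rate. That holds for the missing-assessment exclusion; the valid-baseline condition can act in either direction.

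**Conclusion.** The inconsistency is real, is in current text and should be fixed. The synopsis is the outlier on definition, and the one reported MDS objective response changes status with it: 50% to 12.5% against 0% for k = 2 to 8. This assumes no MDS CR or PR, which is inferred because none is reported, and exact intervals.

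Three stronger readings are not supported:
- That the contrast could be 100% against 0% (k = 1). This does not fit the separate platelet response on the 21-day schedule.
- That the definitions already disagree on timing. No reported response came after Cycle 3.
- That an error rate or power is affected. No test is planned, and only reported rates and intervals change.

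If Phase 2a yields no marrow CR without CR or PR, and every first response falls within both 3 cycles and 3 months, the two definitions give the same Phase 2a count. The SAP text between 2.4.4 and 2.4.6 was not available, so statements about what the SAP omits apply to the rest.

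**What to change.** 1. Replace the synopsis definition with that of Protocol 7.2.3.1 and 8.3.2.1. List the components by disease in SAP 3.3.1. State whether the limit is 3 cycles or 3 calendar months when cycles are delayed.
2. Align the synopsis and Protocol 8.1 and 8.3.2 with SAP 3.3 on one reporting group: Phase 1 by cohort, and Phase 2a at the RP2D and schedule. Show MDS and CMML separately and pooled, and flag Phase 1 RP2D subjects who meet the Phase 2a criteria.
3. Report the rate on all treated subjects (FAS), counting those without a post-treatment assessment as non-responders, as a stated exception to the no-imputation rule in SAP 2.3.2. Give the PPS rate alongside.
4. Correct Protocol 8.1 to up to 48 subjects in up to 8 cohorts. In Protocol 8.1 and SAP 2.1, describe the 20 as including Phase 1 RP2D subjects who meet the Phase 2a criteria. State the same condition in Protocol 3.2 and the matching synopsis text.

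The cost is wording, one extra row for the PPS rate (with a main rate that may be slightly lower), and rows for the separate and pooled disease layouts. No new patients or procedures are needed.
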